#### 7.6.3 ADDITIONAL REPORTING REQUIREMENTS

Unexpected fatal or life-threatening experiences associated with the use of the study treatment will be reported to FDA as soon as possible, but in no event later than 7 calendar days after initial receipt of the information. All other serious unexpected experiences associated with the use of the study treatment will be reported to FDA as soon as possible, but in no event later than 15 calendar days after initial receipt of the information. All events reported to the FDA will also be reported to Aronora Inc. within 24 hours of reporting.

#### 7.6.4 REPORTING OF PREGNANCY

To ensure participant safety, each pregnancy in a participant on study treatment must be reported within 24 hours of learning of its occurrence. The investigator must report the event to the IRB or other oversight entity per institutional policies/requirements. The PI will assess the event and report to the manufacturer and any other entity as warranted.

The pregnancy should be recorded on a CRF and reported by the Investigator to the Aronora Inc. Pregnancy follow-up should be reported using the same form. Any SAE experienced during pregnancy must be reported. If while on study treatment a participant's sexual partner becomes pregnant, the pregnancy and pregnancy outcomes must also be reported as described above. Consent to report information regarding the pregnancy should be obtained from the pregnant individual.

The investigator must follow the pregnancy to determine outcome, including spontaneous, or voluntary termination, details of the birth, and the presence or absence of any birth defects, congenital abnormalities, or any pregnancy- or childbirth related and/or newborn complications.

## 7.7 STUDY STOPPING RULES

The overall study will be paused, and appropriate authorities (e.g., IRB, Knight Data and Safety Monitoring Committee) notified if the following events occur:

- Life-threatening grade 4 toxicity attributable to protocol therapy that is unmanageable, or unexpected.
- Death suspected to be related to study agent

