## 1.4 POTENTIAL RISKS AND BENEFITS

### 1.4.1 KNOWN POTENTIAL RISKS

The safety profile of xisomab 3G3 in humans is still being established. Xisomab 3G3 functions to inhibit, among others, contact activation of the intrinsic blood coagulation cascade. While inhibition or lack of FXII, PK, and HK do not appear to impair hemostasis, it is not yet known if interference with contact-mediated auto-activation of FXI has clinically relevant antihemostatic consequences. This may interfere with hemostatic function, thus increasing the risk for bleeding. Results of the completed phase 1 study (n = 21), following administration of xisomab 3G3, showed no severe, dose-dependent hemostasis-related adverse effects. As a humanized antibody, participants receiving xisomab 3G3 may develop a variety of acute or delayed allergic reactions, such as rash, edema, urticaria, asthma, blood pressure changes, as well as severe anaphylaxis. No severe allergic reactions to xisomab 3G3 were observed in the phase 1 trial. Refer to investigator brochure for further details.

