## 2.2.2 SECONDARY OBJECTIVES AND ENDPOINTS

Objective	Endpoint	Start	End
To evaluate the safety and tolerability of xisomab 3G3 in cancer patients with a PICC or indwelling catheter	
 
1. Incidence of major and clinically-relevant bleeding [refer to Section 6.1.9.1]
 
2. Incidence of xisomab 3G3-associated toxicities [per CTCAE v5.0]
 
	Administration of xisomab 3G3 (Day 1 ± 2 days)	End of follow-up (Day 60)

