## 3.8 STUDY DISCONTINUATION

This study may be temporarily suspended or prematurely terminated if there is sufficient reasonable cause. Written notification, documenting the reason for study suspension or termination, will be provided by the suspending or terminating party to IRB and manufacturer. If the study is prematurely terminated or suspended, the Investigator will promptly inform the IRB and the manufacturer and will provide the reason(s) for the termination or suspension.

Reasons for terminating the study may include the following:

- Incidence or severity of adverse events, in this or other studies, indicates a potential health hazard to participants.
- Data that are not sufficiently complete and/or evaluable.
- Investigators do not adhere to the study protocol, or applicable regulatory guidelines in conducting the study.
- Participant enrollment is unsatisfactory.
- Submission of knowingly false information from the study site to manufacturer or regulatory authorities.
- Upon instruction by local or other regulatory, or oversight authority.

Study may resume once concerns about safety, protocol compliance, data quality are addressed and satisfy the Sponsor/manufacturer, IRB and/or FDA.

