#### **6.1.9.1 Assessment of Major and Clinically Relevant Non-major Bleeding**

Bleeding will be defined using the International Society of Thrombosis and Hemostasis definition of major bleeding for clinical investigations of anti-hemostatic medicinal products in nonsurgical patients (i.e., fatal bleeding, critical organ bleeding such as CNS bleeding, or bleeding causing a fall in hemoglobin of 20 g/L or more) and clinically relevant non-major bleeding (i.e., bleeding that does not fit the former definition of major bleeding but prompts medical attention).

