## 9. CLINICAL MONITORING

### 9.1 OHSU KNIGHT CANCER INSTITUTE DATA & SAFETY MONITORING PLAN

This study is under the oversight of the Knight Cancer Institute's Data Safety and Monitoring Committee (DSMC) as described in the Knight's institutional Data and Safety Monitoring Plan (DSMP). The Knight DSMP outlines the elements required to ensure the safety of clinical trial participants, the accuracy and integrity of the data and the appropriate modification of cancer-related clinical trials for which significant benefits or risks have been discovered or when the clinical trial cannot be successfully concluded. The Knight DSMP also describes the methods and procedures for ensuring adequate oversight of cancer-related research at OHSU.

As described in the Knight DSMP, regardless of a trial's risk level and any specific Knight oversight in place, the Investigator is singularly responsible for overseeing every aspect of the design, conduct, and final analysis of his/her investigation.

The Knight DSMC reviews and monitors study progress, toxicity, safety, and other data for this study. The DSMC will address any issue that raises questions about data integrity or trial participant safety with the Investigator and study team. Should any major concern arise, the Knight DSMC may recommend corrective action, and determine whether to suspend or terminate the study.

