The Knight DSMC evaluates each protocol to determine the risk profile of the trial design. This assessment establishes trial reporting requirements commensurate with risk, and also directs the scope and frequency of Quality Assurance audits. The DSMC may adapt report and audit requirements at any time, if indicated (refer to the Knight DSMP for additional details on reporting and audit frequency). The Investigator will submit trial-specific data reports for the DSMC to assess toxicity and safety data; the report must provide the DSMC with such information as: up-to-date participant accrual; treatment regimen information; current dose level information; AEs and SAEs reported by category; summary of any death on study; unexpected AEs that have been reported; AEs of special or clinical interest; deviations from the approved protocol; that have been reported eligibility exceptions; any inspection, audit, or monitor report; publications and/or developments that may affect scientific validity, subject safety or the ethics of the trial, and a summary of trial status. The study team will provide other information (e.g. scans, laboratory values) upon request.

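### Section 7.7 requires no pause or DSMC notice for related, non-fatal major bleeds below grade 4, and bleeds attributed to the anticancer regimen may go unrecorded

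*Combined protocol and SAP*

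**What the plan says.** Section 7.7 lists two events that oblige a pause and notification. One is "Life-threatening grade 4 toxicity attributable to protocol therapy that is unmanageable, or unexpected". The other is a death suspected to be related to the study agent. The section names no bleeding term, no count and no deadline.

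Section 6.1.9.1 defines major bleeding by its own criteria, not by CTCAE grade: fatal bleeding, critical-organ bleeding, or "bleeding causing a fall in hemoglobin of 20 g/L or more". The first safety endpoint in 2.2.2 is "Incidence of major and clinically-relevant bleeding", and 8.2.3 reports its incidence with a 95% CI in the safety set. On the drug itself, 1.4.1 says "it is not yet known if interference with contact-mediated auto-activation of FXI has clinically relevant antihemostatic consequences".

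Other safety routes are written down:

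- Section 9.1: "The DSMC will address any issue that raises questions about data integrity or trial participant safety". On the investigator's data reports, "the report must provide the DSMC with such information as" AEs and SAEs by category. The committee can suspend the study. For timing the reader is told to "refer to the Knight DSMP for additional details on reporting and audit frequency".
- Section 3.8 permits suspension, and one listed reason is "Incidence or severity of adverse events, in this or other studies, indicates a potential health hazard to participants".
- Sections 7.6.1 to 7.6.3 set IRB and FDA reporting duties.

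On recording, 6.1.9 does not collect known AEs of the planned anticancer regimen, apart from grade 3-4 thrombocytopenia. Section 7.5 leaves out AEs definitely attributable to that regimen.

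**The concern.** The hazard the protocol itself singles out has no trigger of its own. The phase 1 experience summarised in 7.4.1 covers 16 drug-treated subjects, all from a healthy-volunteer trial (1.2.3). This trial doses cancer patients around a catheter insertion, lets anticancer therapy start two days later, and allows standard anticoagulation alongside the drug if the treating physician thinks it warranted (5.1, 5.3.3).

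Each participant receives one dose, so a pause can protect only those not yet dosed. What matters is how soon the DSMC learns of a bleed and whether it sees bleeds accumulating.

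The recording exclusion raises a second issue. A major bleed put down to chemotherapy might not reach the case report form. It would then be missing both from what the DSMC sees and from the incidence in 8.2.3, which is not restricted to drug-related bleeds.

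**Working it through.** Section 7.7 states no number, so there is no plan figure to reproduce. The check is mainly one of reading the sections against each other.

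**1. Can a major bleed fall outside both triggers?** Take a bleed with a 20 g/L hemoglobin fall that is possibly related (7.2.5), not fatal and not life-threatening. It is major under 6.1.9.1. It is not a death, and on the general scale in 7.2.4 it can sit below grade 4, which is reserved for life-threatening consequences or urgent intervention. Neither trigger applies. Because 7.7 has no count, neither applies to a series of such bleeds: any number from 1 to 50 leaves 7.7 silent. A related grade 4 bleed that is both manageable and expected also escapes.

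**2. Do the other routes oblige prompt notice to the DSMC?**

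- 3.8: suspension is permitted, not required, with no count or time limit.
- 9.1: the DSMC receives safety data and may suspend, but report timing is left to the institutional plan, which is not among the documents.
- 7.6.2: SAEs with suspected association go to FDA. The DSMC is not named as recipient.
- 7.6.3: unexpected fatal or life-threatening associated events go to FDA within 7 calendar days and other serious unexpected ones within 15, then to the manufacturer within 24 hours. The event must be unexpected. Under 7.3 that is the sponsor-investigator's judgement, and because 1.4.1 already mentions bleeding risk, a bleed could be judged expected.
- 7.6.1: IRB prompt reporting, including new or increased risks that require a protocol or consent change.

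None requires prompt DSMC notice of a major bleed judged expected.

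**3. What can unrecorded bleeds do to the estimate?** Assume all 50 planned participants are dosed. Each participant whose only qualifying bleed is not recorded lowers the incidence by 1/50 = 2 percentage points. As an example, with exact (Clopper-Pearson) intervals, an assumption because 8.2.3 names no method:

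- 3 of 50 = 6.0%, 95% CI 1.3% to 16.5%
- 2 of 50 = 4.0%, 95% CI 0.5% to 13.7%

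**4. Would a fixed pause count be a clear improvement?** Let X be the number of related major bleeds, binomial with n = 50 and rate p. The documents give no rate for this drug. The values of p are illustrations: 4.9% is the upper figure in 1.1 for patients on therapeutic anticoagulation, and 2% and 10% are assumptions.

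| Pause at | p = 2% | p = 4.9% | p = 10% |
|---|---|---|---|
| 2 bleeds | 26% | 71% | 97% |
| 3 bleeds | 8% | 45% | 89% |
| 4 bleeds | 2% | 23% | 75% |

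The entries are P(X ≥ count). Given that a third bleed occurs within 50, the median number dosed at that point (truncated negative binomial, ignoring the lag from dose to bleed) is 38, 34 and 25. If the pause at 3 became permanent, the expected number spared dosing, the sum over t from 3 to 50 of (50 − t) × P(third bleed at participant t), is 1.1, 7.7 and 21.5. Multiplying by p gives about 0.02, 0.4 and 2.2 bleeds avoided.

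**The case against.** The strongest reply is that this is a small, single-centre, single-dose trial in which qualitative discretion is stated twice (3.8 and 9.1), no two sections conflict, and a related serious bleed might well be judged unexpected. Phase 1 showed no severe dose-dependent hemostatic effects (1.4.1), and the event summary in 7.4.1 names no bleed, so the 15-day FDA report could apply. The DSMC may also already have set its own reporting times. All of this stands. It narrows the point to DSMC notice of bleeds judged expected, and to what 7.7 itself requires.

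On recording, a bleed judged possibly related to the study drug is not definitely attributable to the regimen, so 7.5 already captures it. Footnote F of the schedule in 6.9 includes bleeding in AE evaluation, and 7.5 also asks for AEs to be documented regardless of relationship. This weakens the concern but does not remove it: the exclusions in 6.1.9 and 7.5 are explicit, and neither makes an exception for bleeding.

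Two stronger readings are tempting. A reader might infer that bleeding goes unmonitored, or that timing rests only on routine reports and discretion. The documents do not support that, given the DSMC's remit and the duties in 7.6.1 to 7.6.3. A reader might also infer that a numerical stopping boundary is missing and must be added. The table does not support that: at 4.9% a count of 3 pauses the trial less than half the time, at a median of 34 already dosed, and the gain is material only near the assumed 10%.

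**Conclusion.** The point holds in this limited form. Section 7.7 forces no pause or notice for related, non-fatal major bleeds below grade 4, in any number, and no other route in the documents guarantees that the DSMC hears promptly of one judged expected. The exclusions in 6.1.9 and 7.5 can also understate the incidence in 8.2.3, by 2 points per missed participant if 50 are dosed.

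The practical size of the notification gap cannot be stated. Planned accrual is 50/36 = 1.4 participants a month (3.5), but the DSMC report interval is not in the documents and no major-bleed rate for the drug is given. If the institutional plan already requires prompt notice of major bleeds, only the recording issue and the silence of 7.7 remain. This is a worthwhile, inexpensive improvement and not a defect that undermines the trial. Confidence is moderate.

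**What to change.** Add to 7.7: *Every bleed meeting the 6.1.9.1 definition of major bleeding with onset after xisomab 3G3, through Day 60, is reported to the Knight DSMC within 7 calendar days of the investigator learning of it, with a running count, whatever its CTCAE grade, expectedness or attributed cause. The DSMC decides whether to pause dosing.*

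Add to 6.1.9 and 7.5: *Major and clinically relevant non-major bleeds are always recorded, whatever the attributed cause.*

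The 7 days matches the shortest FDA limit in 7.6.3. A fixed pause count, for example three related major bleeds, is an option the DSMC may set after weighing the figures above. It is not a required change.

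The cost is three short insertions and a little extra reporting and recording. Capture will still be incomplete. Protocol hematology is drawn at screening only (6.9), so a 20 g/L fall will be found mostly through routine-care counts. Follow-up also ends when off-study anticoagulation starts (6.7), after which 7.5 asks only for SAEs assessed as related.

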## 8. STATISTICAL CONSIDERATIONS

Refer to Section 2.1, *Description of the Study Design* for a detailed description of the study design and endpoints.

### 8.1 ANALYSIS POPULATIONS

An intent to treat (ITT) analysis set consists of all participants who consent and enroll in the trial regardless of whether they are exposed to the study drug. An efficacy analysis set consists of participants who have placement of a catheter, receive xisomab 3G3 within 48 hours of catheter placement, and have at least one CAT assessment (i.e., ultrasound and physical exam) by Day 18 of the study. A safety analysis set consists of all participants who are exposed to the single dose of study drug.

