A total of 50 participants are planned for enrollment into this study. Eligibility will be confirmed prior to planned PICC line placement or indwelling central venous catheter placement. Eligible participants that are scheduled to have a catheter inserted as part of their planned anticancer therapy will be enrolled to receive xisomab 3G3. Within 48 hours of insertion of the PICC or indwelling catheter (i.e.  $\pm$  2 days) per institutional standards, participants will undergo IV placement and receive a single dose of xisomab 3G3. Standard procedures for catheter maintenance for sterility and patency will be performed each time the catheter is accessed for use including 10 to 20 ml of normal saline pulsatile flush before and after use and every 7 days in the outpatient setting. Two days after administration of xisomab 3G3 participants may proceed with planned, standard-of-care anticancer treatment in consultation with their treating physician and in accordance with institutional guidelines. The **primary objective** is to measure the efficacy of xisomab 3G3, as determined by the incidence of ultrasound-confirmed CAT (both symptomatic and asymptomatic) within 18 days after catheter insertion, compared to historical cancer controls. All participants will undergo duplex venous ultrasound and physical examination to evaluate symptomatic or asymptomatic CAT at 14 ( $\pm$  4) days after catheter placement. If participants develop symptoms suggestive of CAT such as arm pain, swelling, or erythema in the arm with the PICC, those participants will undergo standard-of-care workup with a unilateral extremity duplex venous ultrasound in the affected arm or leg. Participants that have confirmed CAT or other thrombosis found on imaging, per investigator assessment, will be treated at the discretion of their treating physician per institutional guidelines and standards of care. The duplex venous ultrasound assessment will include evaluation of disease history and physical exam to further assess possible thrombosis-associated symptoms. The **secondary objective** is to establish the safety and tolerability of xisomab 3G3 administered near the time of central line placement in patients that are diagnosed with and treated for solid tumors. All participants will be followed for 60 days (or until resolution/stabilization of any clinically significant drug-related adverse event) from time of catheter insertion to assess for AEs and medication use.

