### 2.2 STUDY OBJECTIVES AND ENDPOINTS

#### 2.2.1 PRIMARY OBJECTIVE AND ENDPOINT

Objective	Endpoint	Start	End
To determine the efficacy of xisomab as measured by the incidence of CAT in individuals with a central venous catheter	Incidence of CAT	Catheter insertion (Day 1)	Day 18

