### **3.5 PARTICIPANT SCREENING AND ENROLLMENT**

In order to participate in this study, signed informed consent must be obtained from the participant or the participant's legally acceptable representative. The current Institutional Review Board (IRB) approved informed consent must be signed and dated by each participant prior to undergoing any study procedures or before any prohibited medications are withheld from the participant in order to participate in this study.

Screening will begin once the participant has provided written informed consent to participate in the study . All screening and baseline evaluations will be performed during the screening phase (i.e., up to 28 days before catheter placement). Day 1 of the clinical trial will be when the central venous catheter is inserted. Total accrual of all participants is anticipated to take a total of 36 months.

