## 5. TREATMENT PLAN

### 5.1 DOSAGE AND ADMINISTRATION

Treatment will be administered on an *out-patient* basis. Reported adverse events and potential risks are described in Section 7.4, Adverse Event List.

Regimen Description			
Agent	Dose	Route**	Schedule
Xisomab 3G3	2 mg/kg	IV (via catheter)	Single dose administered within 48 hours of catheter placement ( $\pm$ 2 days).

\*\*Study drug should be administered as a slow bolus (approximately 1 minute).

Enrolled participants will receive a single fixed dose of xisomab 3G3 (2 mg/kg) through a peripheral IV or the inserted catheter within 48 hours of catheter placement (i.e.  $\pm$  2 days). If Xisomab 3G3 is administered prior to D1 catheter placement, eligibility must be confirmed prior to study drug administration. Participants will be monitored for at least 1 hour on the day of xisomab 3G3 administration for adverse events. Participants not receiving study drug or catheter placement as scheduled, may be rescheduled if within allowable screening window (i.e., no more than 28 days from consent). Participants receiving study drug but have a delay in placement of the catheter beyond 48 hours from time of xisomab administration, will not be considered evaluable for efficacy analysis (per Section 8.1), but will be followed for xisomab 3G3-associated toxicities (per Section 6.7).

Two (2) days after participants receive study drug they may proceed to undergo planned anticancer therapy per standard of care. Administration of planned cancer-directed therapy may not occur earlier than 2 days from time of giving study drug. The type(s) and frequency of administration of anticancer drug(s) comprising the participants' anticancer treatment regimen is at the discretion of treating physician and should be recorded in the CRF.

Consistent with institutional standards, participants may at any time during the study receive a standard of care workup with an ultrasound if they develop symptoms the investigator (or treating physician) believes to be suggestive of CAT, including arm pain and swelling or erythema in the same arm as the catheter. In such cases, the participant may receive antithrombotic therapy, at the discretion of their treating physician, per institutional guidelines.

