## 6.9 SCHEDULE OF EVENTS

Visit Days*	Screening**	On-Study Treatment	End of Treatment Visit Day 14 ( $\pm 4$ days)	Follow-Up Day 60 ( $\pm 4$ days)
	Days -28 to -3	Day 1		
Informed consent	X			
Inclusion/exclusion criteria	X			
Catheter placement A		X		
Xisomab 3G3		X		
Medical history	X			
Medication history	X			
Physical Examination C	X	X G	X	
Radiographic Imaging		Per investigator's discretion, as clinically indicated		
Ultrasound D			X	
Hematology	X			
Biochemistry	X			
Coagulation	X		X	
Pregnancy test E	X			
AE assessment and Conmeds B,F	X	X	X	X
Research blood draw/Assessment for Immunogenicity H	X	X	X	
Electrocardiogram I	X	As clinically indicated		

\* Ideally the clinic visit and all the study requirements should be performed as indicated.

\*\* Enrolled participants will receive a single fixed dose of xisomab 3G3 (2 mg/kg) through a peripheral IV or the inserted catheter within 48 hours of catheter placement (i.e.  $\pm 2$  days). If Xisomab 3G3 is administered prior to D1 catheter placement, eligibility must be confirmed prior to study drug administration.

A Placement of the catheter in participants will be performed according to institutional guidelines. Ultrasound may be used to guide the placement of the catheter, and may include use of local anesthetic.

B For concomitant medications – enter new medications started during the trial through the end of treatment visit.

C All physical exams will include assessing vital signs, weight and ECOG performance status.

D Per institutional standards, study participants will be evaluated for CAT via planned ultrasound 14  $\pm 4$  days after catheter insertion. Additional ultrasound evaluations may occur at any time during the study based on treating physician and PI discretion; however, only ultrasounds performed within 18 days from catheter placement will be included when computing CAT incidence. Ultrasound to occur as part of EOT, prior to provider visit.

E For women of reproductive potential, a serum pregnancy test should be performed within 3 days prior to first dose of trial treatment. Serum pregnancy test should be performed by the local study site laboratory per institutional guidelines, and repeated if required.

Visit Days*	Screening**	On-Study Treatment	End of Treatment Visit Day 14 ( $\pm 4$ days)	Follow-Up Day 60 ( $\pm 4$ days)

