#### 8.2.2 ANALYSIS OF PRIMARY ENDPOINT

Using the efficacy analysis set, the incidence of ultrasound-detected CAT (including both symptomatic and asymptomatic clots) in the first 18 days after catheter insertion will be assessed and reported with a 95% CI. CAT incidence will also be separately estimated for each general catheter type (i.e., PICC vs. indwelling port).

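### The efficacy set has no earliest scan day, the scan cut-off is written in two day conventions, and no bounds are planned for participants without a scan

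*Combined protocol and SAP*

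**What the plan says.** **Entry to the efficacy set.** Section 8.1 requires a catheter, drug within 48 hours of placement, and that participants "have at least one CAT assessment (i.e., ultrasound and physical exam) by Day 18 of the study". It gives a latest day only.

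**Which scans count.** Footnote D of section 6.9 states that "Additional ultrasound evaluations may occur at any time during the study based on treating physician and PI discretion", and then that "only ultrasounds performed within 18 days from catheter placement will be included when computing CAT incidence". It has no lower limit either. Section 5.1 adds that "participants may at any time during the study receive a standard of care workup with an ultrasound if they develop symptoms".

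**The planned scan.** Section 2.1: "All participants will undergo duplex venous ultrasound and physical examination to evaluate symptomatic or asymptomatic CAT at 14" (±4) days after placement. Section 6.1.8 says the same, counted from placement. Sections 5.2, 6.5 and 6.6 and the column header in 6.9 label the visit Day 14 (±4 days).

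**Day numbering.** Section 3.5: "Day 1 of the clinical trial will be when the central venous catheter is inserted". Section 2.2.1 agrees, and both it and the Synopsis end the primary endpoint at Day 18.

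**Analysis.** Section 8.2.2 uses the efficacy set, and the incidence of ultrasound-detected CAT "in the first 18 days after catheter insertion will be assessed and reported with a 95% CI".

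**Missing data.** Section 8.4 allows full or partial exclusion in consultation with the biostatistician, imputes nothing, and requires each analysis to state its sample size and the reasons for exclusion. Under 6.6, a participant who dies or enters hospice before the end of treatment visit does not have that visit.

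**The concern.** The primary result is one proportion with a 95% CI in about 48 people, set against an assumed 60% historical rate. Three wording gaps affect who is in the denominator and who is called CAT-free.

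1. *No earliest day.* A scan done for symptoms in the first days, negative and not followed by the planned scan, can satisfy 8.1 if a physical exam goes with it. The participant then enters an 18-day incidence as a non-event. Section 1.1 puts the mean time from PICC insertion to thrombosis at 8-11 days, so an early negative scan cannot establish 18 days without CAT. The error runs in the drug's favour.
2. *Two day conventions.* A participant whose only scan is exactly 18 days after placement is inside footnote D and 8.2.2 but outside 8.1.
3. *No scan.* These participants leave the analysis, and no range for what they might have contributed is planned. The direction of that effect is unknown.

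**Working it through.** **The plan's own figure.** Inputs from 8.3.1: 60% against 40%, two-sided α 0.05, power 80%, 4% ineligible for efficacy. By the normal approximation, n = (1.960 + 0.842)² × 0.24 / 0.20² = 47.1, so 48; 48 / 0.96 = 50. The planned 50 reproduces, and 48 is the expected efficacy set. Intervals below are exact (Clopper-Pearson), since 8.2.2 names no method. The plan states no formal test, so whether an interval excludes 60% is only a way of reading the planned CI.

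**Early-only scans.** Let f be the share of the efficacy set whose only scan precedes the window, s the proportion of 18-day CAT that such a scan detects, and 60% the true rate in everyone. Neither f nor s is in the documents; both are assumptions.

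Reported rate = 0.60(1 − f) + 0.60·s·f

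| f | s = 0.25 | s = 0.50 | s = 0.75 |
|---|---|---|---|
| 1/48 | 59.1% | 59.4% | 59.7% |
| 2/48 | 58.1% | 58.8% | 59.4% |
| 5% | 57.8% | 58.5% | 59.3% |

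The largest shift is about 2.2 points. For comparison, the interval for 21/48 runs from 29.5% to 58.8%, about 29 points wide.

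If early-only negatives are removed and early positives kept, the rate is [0.60(1 − f) + 0.60·s·f] / [1 − f(1 − 0.60s)]. At f = 5% this gives 60.3%, 60.6% and 60.9% for s = 0.25, 0.50 and 0.75: a smaller error, in the opposite direction.

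**Day conventions.** With insertion as Day 1, study day = days after placement + 1.

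| Wording | Days after placement | Study days |
|---|---|---|
| 14 ±4 days after placement (2.1, 6.1.8, footnote D) | 10 to 18 | 11 to 19 |
| Within 18 days of placement (footnote D, 8.2.2) | up to 18 | up to 19 |
| Day 14 (±4 days) (5.2, 6.5, 6.6, header of 6.9) | 9 to 17 | 10 to 18 |
| Day 18 limit (Synopsis, 2.2.1, 8.1) | up to 17 | up to 18 |

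The conventions differ by one day at each end of the window. Section 6.6 combines them, attaching the Day 14 (±4 days) label to time after placement.

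The number of scans exactly 18 days after placement is not in the documents. If scans spread evenly over the nine days, it is 48/9 = 5.3; if they cluster at 14 days with SD 2 (assumed), about 1.4. Two threshold examples show what excluding them could do:
- One CAT-positive dropped: 22/48 = 45.8% (31.4-60.8) becomes 21/47 = 44.7% (30.2-59.9).
- Two negatives dropped: 21/48 = 43.8% (29.5-58.8) becomes 21/46 = 45.7% (30.9-61.0).

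These are unlikely: with exactly one such scan, the first needs a count of exactly 22 and that scan positive, about 3.8% at a true 40%.

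**Unscanned participants.** Suppose the whole planned 4% (2 of 50) were unscanned. Counting both as CAT moves the upper limit past 60% only at a count of 21: 21/48 = 43.8% (29.5-58.8) against 23/50 = 46.0% (31.8-60.7). The chance of that count is 10.0% at a true 40% and 0.9% at a true 60%. With 5 unscanned, an assumption above the planned rate, 19/45 = 42.2% (27.7-57.8) becomes 24/50 = 48.0% (33.7-62.6) at worst and 19/50 = 38.0% (24.7-52.8) at best. Counts where the worst case matters (18 or 19) then have probability 23.5% at a true 40% and 1.0% at a true 60%.

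**The case against.** **The visit label agrees with 8.1.** The end of treatment visit is repeatedly labelled Day 14 (±4 days), which ends on Day 18, as do 8.1 and the endpoint in the Synopsis and 2.2.1. This stands. A reader might infer that 8.1 simply cuts off one day of the scan window. The documents do not support that: it is true against one wording and false against the other.

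**The early-only case is an inference.** Every participant is due an ultrasound with physical exam in the window, and 8.1's description of a CAT assessment matches that visit. An early-only negative needs an early scan with an exam, a negative result and a missed planned scan. The 5-7% in section 1.1 counts patients who develop symptomatic thrombosis, so it does not measure this share. All of that stands and keeps the effect small. But 8.1 asks for at least one assessment by a date, and neither it nor footnote D ties that assessment to the window.

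**Discretion.** A reader might infer that doubtful cases would be settled once results are known. Section 8.4 gives discretion but does not mention timing, so that inference goes beyond the text.

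**Bounds are optional in a phase 2 estimation study.** Section 8.4 already requires the sample size and exclusion reasons, so a reader could derive bounds. Also, the 4% is total efficacy ineligibility, including placement delayed beyond 48 hours, so 2 of 50 probably overstates the unscanned. Both points stand. They reduce the weight of this part, but the bounds are still not pre-specified.

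**Conclusion.** The point holds and is minor. As written, sections 8.1, 6.9 and 8.2.2 allow a participant whose only scan was negative before the planned window to be counted as CAT-free for the first 18 days. The error favours the drug. Its expected size is small: a true 60% reads 57.8-59.3% at an assumed 5% share and 25-75% detection, with the same underlying rate in those participants.

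The cut-off problem is two unreconciled day conventions, and at the upper end it matters only for a participant whose sole scan falls exactly 18 days after placement. The lack of bounds is a reporting gap of unknown direction; at the planned ineligibility rate it would change the reading against 60% at a single count.

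The sample size is not in question, and nothing here shows that the trial's conclusion would be wrong.

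**What to change.** 1. **Reconcile the day numbering** in the Synopsis, 2.2.1, 5.2, 6.5, 6.6, 6.9 (column header and footnote D), 8.1 and 8.2.2, so that every in-window scan qualifies for the efficacy set. Changing 8.1 alone would leave the Synopsis and the visit labels in conflict. Do this first, because item 2 depends on where the window starts.
2. **Define the outcome in 8.1.** Count ultrasound-confirmed CAT at any time through the cut-off as an event. Count as CAT-free only those with a negative scan inside the planned window. Treat early-only negatives as unassessed. Because this rule can bias slightly upward (60.3-60.9% for a true 60% at a 5% share), also report the estimate with them included.
3. **Add a sensitivity analysis** with best-case and worst-case bounds (unassessed counted as no CAT and as CAT) among participants who had a catheter placed and received drug within 48 hours of placement. That restriction keeps the exclusion in 5.1 for placement delayed beyond 48 hours.

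Cost: wording changes and a few extra lines in the primary results table, with possibly one or two fewer evaluable participants. No new visits or procedures are needed.
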